Research question and objectives:	
This protocol is for a series of comparative effectiveness and safety analyses within periodically updated cohorts of patients initiating dabigatran (compared to warfarin) and other new oral anticoagulants (NOAC) (as they become available), compared to warfarin, followed longitudinally for the occurrence of a variety of health outcomes.
 
Objectives
 
 1) Primarily, to conduct direct comparisons over time between dabigatran and warfarin and quantify the association between anticoagulant choice and the occurrence of specific outcomes of interest 2) Secondarily, to monitor the number of people initiating other NOAC medications and, when sufficient, to compare study outcomes between other NOAC medications and warfarin 		
Study design:	Observational sequential cohort study based on existing data		

Name of company: Boehringer Ingelheim	 Boehringer Ingelheim		
Name of product: PRADAXA®			
Name of active ingredient: DABIGATRAN ETEXILATE			
Protocol date: 25 Feb 2014	Study number: 1160.207	Version/Revision: Version 1	Version/Revision date: 25 Feb 2014
Proprietary confidential information © 2014 Boehringer Ingelheim International GmbH or one or more of its affiliated companies. All rights reserved. This document may not - in full or in part - be passed on, reproduced, published or otherwise used without prior written permission			
Population:	Patients with a recorded diagnosis of atrial fibrillation without evidence of valvular etiology who initiate dabigatran (or other NOACs as they become available) compared with warfarin initiators.		
Study data source:	This study will be conducted within both UnitedHealth and Marketscan data sources. The first analyses of this study will include data from October 2010 through December 2012 for the cohort formation and data from July 2008 through September 2010 for disease risk score (DRS) calculation. Both data sources will be updated on a 6-month basis through December 2015		
Expected study size:	
The estimated final study size will be ~ 60,000 dabigatran initiators, matched to ~60,000 warfarin initiators with approximately 24,000 cumulative person-years of observation in each exposure group, and other NOAC initiators (numbers dependent on use) separately matched to a similar number of warfarin initiators.
 
The estimated study size (after PS matching) for interim analyses:
 
Interim report 1 (Apr 2014): ~ 24,000 dabigatran and ~24,000 warfarin initiators with 10,000 PYs of observation in each group
 
Interim report 2 (Jul 2014): ~ 30,000 dabigatran and ~30,000 warfarin initiators with 12,350 PYs of observation in each group
 
Interim report 3 (Nov 2014): ~ 36,000 dabigatran and ~36,000 warfarin initiators with 14,700 PYs of observation in each group
 
Interim report 4 (Mar 2015): ~ 42,000 dabigatran and ~42,000 warfarin initiators with 17,050 PYs of observation in each group
 
Interim report 5 (Sep 2015): ~ 48,000 dabigatran and ~48,000 warfarin initiators with 19,400 PYs of observation in each group
 
Interim report 6 (Mar 2016): ~ 54,000 dabigatran and ~54,000 warfarin initiators with 21,750 PYs of observation in each group
 
Final report (Dec 2016): ~ 60,000 dabigatran and ~60,000 warfarin initiators with 24,100 PYs of observation in each group
		

Name of company:	 Boehringer Ingelheim		
Name of product:	PRADAXA®		
Name of active ingredient:	DABIGATRAN ETEXILATE		
Protocol date:	Study number:	Version/Revision:	Version/Revision date:
25 Feb 2014	1160.207	Version 1	25 Feb 2014
Proprietary confidential information © 2014 Boehringer Ingelheim International GmbH or one or more of its affiliated companies. All rights reserved. This document may not - in full or in part - be passed on, reproduced, published or otherwise used without prior written permission			
Main criteria for inclusion:	
 • A recorded diagnosis of atrial fibrillation. • Initiation of anticoagulant medication (dabigatran (or other NOACs as they become available) or warfarin). • At least 18 years of age on the date of anticoagulant initiation. • CHA₂DS₂-VASc score ≥ 1 		

1. LIST OF ABBREVIATIONS AND TERMS

ACCP	American College of Chest Physicians
ACEI	Angiotensin-converting Enzyme Inhibitor
AES	Advanced Encryption Standard
AF	Atrial Fibrillation
ALT	Serum Alanine Aminotransferase
ARB	Angiotensin Receptor Blocker
ASCVD	Atherosclerotic Cardiovascular Disease
BB	Beta Blocker
BI	Boehringer Ingelheim
BMI	Body Mass Index
CABG	Coronary Artery Bypass Graft
CAD	Coronary Artery Disease
CCB	Calcium Channel Blocker
CHA ₂ DS ₂ -VASc	Congestive Heart Failure, Hypertension, Age > 75, Diabetes Mellitus, Prior Stroke or Transient Ischemic Attack, Vascular Disease, Age 65-74, Sex Category
CHADS ₂	Congestive Heart Failure, Hypertension, Age > 75, Diabetes Mellitus, Prior Stroke or Transient Ischemic Attack
CHF	Congestive Heart Failure
CI	Confidence Interval
CONSORT	Consolidated Standards for Reporting Trials
CPT	Current Procedural Terminology
Cr	Creatinine
DM	Diabetes Mellitus
DRG	Disease
DRS	Disease Risk Score
DVT	Deep Venous Thromboembolism
Dx	Diagnosis-Related Group
ESC	European Society of Cardiology
GFR	Glomerular Filtration Rate
GI	Gastrointestinal
H2 Receptor	Histamine H2 Receptor
HAS-BLED	Hypertension, Abnormal Liver/Renal function, Stroke, Bleeding history or predisposition, Labile INR, Elderly (Age >65), Drugs-Alcohol usage
HbA1c	Hemoglobin A1C
HCPC	Healthcare Common Procedure Coding
hdPS	High-dimensional Propensity Score
HR	Hazard Ratio
ICD-9	International Classification of Diseases, Ninth Revision, Clinical Modification

ICH	Intracerebral Hemorrhage
INR	International Normalized Ratio
ITT	Intent-To-Treat
LDL	Low Density Lipoprotein
LOS	Length of Stay
MDRD	Modification of Diet in Renal Disease
MI	Myocardial Infarction
NOAC	New Oral Anticoagulant
NSAID	Non-steroidal Anti-inflammatory Drug
NVAF	Non-valvular Atrial Fibrillation
PAD	Peripheral Artery Disease
PCI	Percutaneous Coronary Intervention
PE	Pulmonary Embolism
PGP	P-glycoprotein
PPI	Proton Pump Inhibitor
PPV	Positive Predictive Value
PS	Propensity Score
PTCA	Percutaneous Transluminal Coronary Angioplasty
PVD	Peripheral Vascular Disease
PY	Person-Year
RE-LY	Randomized Evaluation of Long-Term Anticoagulation Therapy
RR	Relative Risk
SAH	Subarachnoid Hemorrhage
SCr	Serum Creatinine
SD	Standard Deviation
TIA	Transient Ischemic Attack
US	United States
VTE	Venous Thromboembolism

3. AMENDMENT AND UPDATES

None

4. MILESTONES

Planned dates for the following milestones:

Date	Phase 2		Data Source	
	Milestone	Month	United	MarketScan
			Claims and lab data are released every 6 months in Jan and Jul (6-month lag time)	Claims data are released quarterly in Mar, Jun, Sept, and Dec (9-month lag time) Lab data are released yearly in Dec (12-month lag time)
Jun, 2012	Contract	0		
	Year 1			
Jun, 2013	Draft Protocol	12		
	Year 2			
Jan, 2014	Final Protocol	19		
Apr, 2014	Interim Report 1	22	Data through Dec 2012	Claims through Dec 2012 Labs through Dec 2012
Jul, 2014	Interim Report 2	25	Data through Jun 2013 (Update received in Jan 2014)	Claims through Jun 2013 (Update received in Mar 2014) Labs through Dec 2012 (Update received in Dec 2013)
Nov, 2014	Interim Report 3	29	Data through Dec 2013 (Update received in Jul 2014)	Claims through Sep 2013 (Update received in Jun 2014) Labs through Dec 2012 (Update received in Dec 2013)
	Year 3			
Mar, 2015	Interim Report 4	32	Data through Jun 2014 (Update received in Jan 2015)	Claims through Dec 2013 (Update received in Dec 2014) Labs through Dec 2013 (Update received in Dec 2014)
Sep, 2015	Interim Report 5	39	Data through Dec 2014 (Update received in Jul 2015)	Claims through Sep 2014 (Update received in Jun 2015) Labs through Dec 2013 (Update received in Dec 2014)
	Year 4			
Mar, 2016	Interim Report 6	45	Data through Jun 2015 (Update received in Jan 2016)	Claims through Dec 2014 (Update received in Dec 2015) Labs through Dec 2014 (Update received in Dec 2015)
	Year 4			
Dec, 2016	Final Report	54	Data through Dec 2015 (Update received in Jul 2016)	Claims through Dec 2015 (Update received in Sep 2016) Labs through Dec 2014 (Update received in Dec 2015)

5. RATIONALE AND BACKGROUND

A number of new oral anticoagulants are being developed and marketed to replace vitamin K antagonists, one of the most important drugs in modern medicine. [P11-11875] Unlike vitamin K antagonists, these new drugs do not require dose titration involving intensive therapeutic monitoring of prothrombin time to achieve target anticoagulation within a narrow therapeutic range. In Phase III studies, these drugs were found to be therapeutically advantageous or non-inferior over warfarin. In the coming years, as many as six new anticoagulants could be on the market and a lack of valid comparative evidence will hinder prescriber and payor decision-making.

To date, these drugs have been studied in randomized clinical trials for three separate indications: (1) prevention of stroke and systemic embolism among patients with atrial fibrillation; (2) prevention of deep venous thrombosis (DVT) among patients undergoing hip or knee replacement therapy; and (3) treatment of venous thromboembolism (VTE). Phase III clinical trials comparing dabigatran, rivaroxaban, apixaban, and edoxaban to warfarin in patients with non-valvular atrial fibrillation (NVAF) have been completed. [R11-4190] [P09-11669] [R11-4223] [R13-5082] The objective of this part of the project is to conduct a series of comparative effectiveness and safety studies across the available anticoagulants, starting with warfarin and dabigatran and including additional ones as they become available within data sources available to us at the Division of Pharmacoepidemiology. Such sequential approach will extend Phase I analyses (study protocol 1160.157) by providing greater precision around effect estimates as well as providing an evaluation of their use in actual practice and among subgroups of patients that were not represented in clinical trials. This evaluation will provide a direct assessment of comparative effectiveness and potential adverse events across the anticoagulants that may have eluded the pre-marketing trials.

6. RESEARCH QUESTIONS AND OBJECTIVES

This protocol is for a series of comparative effectiveness and safety analyses within periodically updated cohorts of patients with NVAF at risk for stroke initiating dabigatran or other oral NOAC medications as they become available, compared to warfarin, followed longitudinally for the occurrence of a variety of health outcomes.

Specific objectives of this active surveillance program are:

- 1) Primarily, to conduct direct comparisons over time between dabigatran and warfarin and quantify the association between anticoagulant choice and the occurrence of specific outcomes of interest
- 2) Secondarily, to monitor the number of people initiating other NOAC medications as they become available and, when sufficient, to compare study outcomes between other NOAC medications and warfarin.

7. RESEARCH METHODS

7.1 STUDY DESIGN

This study will involve a sequentially built parallel cohort design with propensity score (PS) matching to address potential confounding. Each new data update will provide additional follow-up time on the patients already in the cohort, as well as new initiators who will be matched on PS and calendar quarter of initiation and added to the existing cohort for the cumulative analyses. This study design was selected to facilitate the inclusion of additional subjects and follow-up time as data become available over the course of the study period. The study will be conducted within two US-based longitudinal healthcare claims databases (MarketScan and UnitedHealth Research Database, see also section 6.5 for more details). Cohort selection and all analyses will be performed separately within each database and a combined analysis that pools results from the two databases for the same time periods will be done if appropriate, based on an assessment of homogeneity of treatment effect. Pooling of results across data sources will correspond to a weighted average effect (as in a fixed effects meta-analysis) using the Mantel-Haenszel method. [\[R97-0509\]](#) It is expected that there will be little heterogeneity of treatment effects across the databases since the databases are similar with respect to who is included in the database (employed people and their dependents) and the nature of data captured (health insurance transactions billed on a negotiated fee for service basis). Heterogeneity will be assessed by comparing the treatment effect point estimates across data sources. Assessment of heterogeneity will not rely on a statistical test of heterogeneity, since the large study size may indicate significant heterogeneity ($p < 0.05$) even if estimates are similar (i.e. a difference that is not clinically meaningful) and the purpose of this assessment of heterogeneity is intended only for determining whether it is reasonable to combine data sources. If contrary to expectations, there is a difference $> 30\%$ in the overall effect measure for a primary outcome across the two data sources, we will conduct an additional investigation that assesses treatment effect within levels of protocol-specified subgroups (Section 6.9.2) separately by a database. If treatment effect is different across levels of the subgroup variable within a data source, and the distribution of this subgroup variable differs by data source, then the pooling will be conducted within strata of the subgroup variable or variables across which heterogeneity is observed to account for this heterogeneity.

The primary analyses will involve dabigatran initiators compared to warfarin initiators; as other NOAC medications become available for stroke prevention, we will form additional cohorts of other NOAC medications and separately compare them to warfarin in the secondary analyses once sufficient number of initiators will have accrued. The same (as described below for dabigatran) inclusion/exclusion criteria will apply and a similar set of analyses will be conducted.

7.2 SETTING

Initiators of dabigatran and warfarin from two US data sources: (1) UnitedHealth Research Database and (2) MarketScan Commercial Claims and Encounters database and Medicare supplement between October 2010 and December 2012, with 6-month updates through December 2015. Initiators of other NOAC medications will be added as these medications become available for stroke prevention in NVAF. Data from July 2008 through September 2010 will be used for disease risk score (DRS) calculation.

7.3 SUBJECTS

Patient Selection:

- The main cohort will consist of patients with NVAF at risk for stroke initiating an oral anticoagulant medication in the timeframe of the study
 - warfarin and dabigatran for the primary analysis
 - other NOACs to be added separately in the secondary analysis as they become available for stroke prevention in later time intervals
- Warfarin initiators between January 2009 and September 2010 will be used for estimation of disease risk scores.

Inclusion criteria:

- Initiation of an oral anticoagulant is defined by a dispensing of an anticoagulant medication (warfarin or a NOAC medication) in the source data, with no dispensing of any oral anticoagulant in the prior 12 months. The date of that dispensing will be defined as the index date for that initiation.
- At least one ICD-9 diagnosis code of 427.31 (atrial fibrillation) at any time prior to and including the index date
- At least 12 months (365 days) continuous enrollment, defined as ≤ 32 days enrollment gap using enrollment and disenrollment dates, preceding the index date
- 18 years of age and older at index date
- CHA₂DS₂-VASc score ≥ 1

Exclusion criteria:

- Patients with missing or ambiguous age or sex information
- Patients with a nursing home stay during baseline
- Patients with a dispensing of any oral anticoagulant during the 12 months preceding and including the index date
- Patients with documented evidence of valvular disease defined as at least 1 inpatient or outpatient ICD-9 Dx code of [\[R11-4334\]](#)
 - 394.x (diseases of mitral valve)
 - 395.x (diseases of aortic valve)
 - 396.x (diseases of mitral and aortic valve)
 - 397.x (diseases of other endocardial structures)
 - 398.9x (other and unspecified rheumatic heart diseases)
 - V42.2 (heart valve replaced by transplant)
 - V43.3 (heart valve replaced by a mechanical device/prosthesis)

OR

ICD-9 procedure code 35.1x (open heart valvuloplasty without replacement), 35.2x (replacement of heart valve) [\[R03-1232\]](#)

OR

one of the following CPT codes:

33660-33665 (atrioventricular valve repair)
33400-33403 (aortic valve valvuloplasty)
33420-33430 (mitral valve repair/valvuloplasty/replacement)
33460 (valvectomy, tricuspid valve, with cardiopulmonary bypass)
33463-33468 (tricuspid valve repair/valvuloplasty/replacement)
33475 (replacement, pulmonary valve)
33496 (prosthetic valve dysfunction repair)
0257T (implantation of catheter-delivered prosthetic aortic heart valve; open thoracic approach)
0258T (transthoracic cardiac exposure for catheter-delivered aortic valve replacement; without cardiopulmonary bypass)
0259T (transthoracic cardiac exposure for catheter-delivered aortic valve replacement; with cardiopulmonary bypass)
0262T (implantation of catheter-delivered prosthetic pulmonary valve, endovascular approach)

at any time prior to and including the index date.

We will balance baseline covariates among patients initiating each drug by means of a multivariate confounder summary score (by matching on the exposure propensity score, with confounder balance assessed by the disease risk score). [\[R12-1912\]](#)

Cohort formation

We will receive new data as they become available on a periodic basis (every 6 months) and we will update the study cohorts through December 2015. Initiators of oral anticoagulants identified in each data cut, as previously described, will form sequential cohorts.

In each sequential cohort we will balance baseline covariates among patients initiating each drug by matching on the exposure propensity score and calendar quarter of initiation. Patients' follow-up will end when there is a treatment gap of ≥ 14 days from the end of calculated days supplied. Patients will be allowed to contribute only once.

[figure not shown]

Figure 1

Patient Selection Flow

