7.4 VARIABLES

7.4.1 EXPOSURES

Table 1 Market availability for the treatments of interest

Class	Drug	FDA approved*	FDA approved for stroke prevention in patients with non-valvular atrial fibrillation at risk for stroke
Direct thrombin inhibitors	Dabigatran	19 October 2010	19 October 2010
Direct Xa inhibitors	Rivaroxaban	1 July 2011	4 November 2011
	Apixaban	28 December 2012	28 December 2012

Table 1 (con't)

Market availability for the treatments of interest

Edoxaban	Phase III	N/A
Otamixaban	Phase III	N/A
Betrixaban	Phase II	N/A

*as of December2013

The primary contrast of interest is between new initiators of warfarin and new initiators of dabigatran, defined as no anticoagulation with *any oral anticoagulant* in the 12 months before the index prescription.

In the secondary analysis and as they become available for stroke prevention in NVAF patients, other NOAC medications will be compared to warfarin. The same definitions and inclusion/exclusion criteria will be applied.

Concomitant therapy with medications that are not cohort-defining medications (defined as simultaneous use on the day of dabigatran or warfarin initiation) will be accounted for in the study analyses as a covariate and used for balancing or stratification.

Study follow-up

We will follow patients for each of the outcomes of interest in a prospective manner and we will estimate measures of effect using person-time based analyses.

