The primary analyses will use an 'as treated' approach. Follow-up will start the day after cohort inclusion, which is the day of treatment initiation, and will end at the time of disenrollment, end of the observation period (available data), death, admission to a nursing home, discontinuation of the index study exposure, or switch to a different anticoagulant whichever comes first. Exposure will be considered discontinued if there is a treatment gap ≥ 14 days from the end of calculated days supplied. Warfarin therapy involves dose titration following initiation before a stable therapeutic INR is obtained. We will use the reported days' supply as a proxy for duration of exposure following a dispensing as it may more adequately reflect the use pattern within a commercial health insurer database represented by UnitedHealth and MarketScan. This approach involves a potential mismatch between the presumed exposure derived from dispensing data and actual exposure. The utilization study (described in study protocol 1160.177) will inform the sensitivity analyses around this assumption and seek to clarify how sensitive results are to variations in the exposure assumption. Switchers will be censored in the as-treated approach on the day of the dispensing of the alternative medication. If switching was the consequence of a side effect of a drug, most likely the index drug was discontinued for some time before the new drug was initiated. Any clinical event therefore was most likely recorded during that period and will be

attributed to the index drug.

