7.4.2 OUTCOME(S)

The primary outcomes of interest include stroke (hemorrhagic, ischemic, uncertain classification) and major bleeding. Secondary outcomes are: stroke or systemic embolism, , transient ischemic attack (TIA), myocardial infarction (MI), venous thromboembolism (VTE), deep vein thrombosis (DVT), pulmonary embolism (PE).

Systemic embolism (defined as an acute vascular occlusion of the extremities or any organ, such as kidneys, mesenteric arteries, spleen, retina or grafts), ischemic stroke, hemorrhagic stroke, stroke of uncertain classifications, major intracranial bleeding, major extracranial bleeding, major gastrointestinal (GI) bleeding, major upper GI bleeding, major lower GI bleeding, major urogenital bleeding, major other bleeding. Further outcomes include hepatotoxicity and all-cause mortality.

As mortality data in the commercial databases is currently limited to inpatient deaths, we will seek to improve the ascertainment of the death outcome through external linkage, such as with the Social Security Death Master File.

Table 2 **Outcome Definitions**

Outcome	Hospital Discharge Code(s)	Comments
Primary Outcomes		
Stroke	As primary ICD-9 discharge diagnosis (Dx): 431.x Intracerebral hemorrhage (ICH) 433.x1 Occlusion and stenosis of precerebral arteries with cerebral infarction 434.x1 Occlusion and stenosis of cerebral arteries with cerebral infarction 436.x Acute, but ill-defined cerebrovascular events	See Mini-Sentinel report for PPV for individual codes or other algorithms [R14-0052]
Major hemorrhage	Major intracranial bleeding, major extracranial bleed (for codes see component outcomes below)	
Secondary outcomes		
Stroke or systemic embolism	Stroke or systemic embolism (for codes see component outcomes below)	

Table 2 (con't)

Outcome Definitions

Outcome	Hospital Discharge Code(s)	Comments
Systemic embolism	ICD-9 Diagnoses: 444.x Arterial embolism	No validation studies available. Codes are thought to be specific because of the substantial clinical symptomatic and required therapy.

Table 2 (con't) Outcome Definitions

Ischemic stroke	As primary ICD-9 discharge diagnosis (Dx): ICD-9 Dx 433.x1 Occlusion and stenosis of precerebral arteries with cerebral infarction ICD-9 Dx 434.x1 Occlusion and stenosis of cerebral arteries with cerebral infarction	PPV 95.5% in commercially-insured population for the codes in any position [R11-4887] Use of codes in the primary position generally increases the PPVs [R14-0052]

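### One AF code at any past time lets in anticoagulant starts for a current VTE or joint replacement, so unless matching balances these the VTE, DVT and PE results may lean toward dabigatran

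*Combined protocol and SAP*

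**What the plan says.** Section 7.3 defines the population as follows: "The main cohort will consist of patients with NVAF at risk for stroke initiating an oral anticoagulant medication in the timeframe of the study". The diagnosis is established by "At least one ICD-9 diagnosis code of 427.31 (atrial fibrillation) at any time prior to and including the index date". There is no rule on recency, care setting, code position or repeat codes, and nothing links the index dispensing to AF. The exclusions cover missing or ambiguous age or sex, a nursing home stay, prior oral anticoagulant use and valvular disease.

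Section 5 states that "these drugs have been studied in randomized clinical trials for three separate indications": stroke prevention in AF, DVT prevention at hip or knee replacement, and VTE treatment. Table 1 in 7.4.1, dated December 2013, reads "Dabigatran 19 October 2010 19 October 2010" for first approval and AF approval. For rivaroxaban the two dates differ (1 July 2011 and 4 November 2011).

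Section 7.4.2 lists VTE, DVT and PE as secondary outcomes. On timing, 7.4.1 says: "Follow-up will start the day after cohort inclusion, which is the day of treatment initiation".

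**The concern.** A patient with an old AF code who starts warfarin for a new DVT, or after a knee replacement, meets every visible criterion. If such starters fall mainly in one arm, the two groups differ in their reason for treatment.

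The consequence is most direct for VTE, DVT and PE. A later admission that codes the index clot again, or a true recurrence, would count as an outcome. Both would fall mainly on warfarin, which would make dabigatran look better at preventing VTE than it is.

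**Working it through.** **1. Is the path open in the visible text?** Four statements, side by side:

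- Eligibility (7.3): one AF code at any earlier time, and no exclusion for recent VTE or joint surgery.
- Drug (Table 1): no non-AF approval date for dabigatran as of December 2013, so other-indication starts are expected mainly on warfarin.
- Timing (7.4.1): follow-up begins the next day, with no stated lag.
- Outcome (Table 2): the DVT and PE rows state no new-event requirement, and the algorithm cited for DVT used discharge codes in any position. By contrast, the MI row removes subsequent-episode codes, and the stroke rows require the primary position.

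**2. Do the visible safeguards close it?**

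- The disease risk score balance check (7.6) is for the primary outcomes only.
- If a standardized difference exceeds 0.1, the fallback (7.9.1) adjusts for HAS-BLED and CHA2DS2-VASc. As spelled out in Section 1, neither names VTE or joint surgery.
- The propensity score uses all pre-defined covariates, but the list (cited as Section 6.4.3) is not in the text available. Whether it holds recent VTE or joint surgery cannot be read.

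**3. How large could it be?** The plan gives no VTE rate and no share of starters with another indication, and Table 8 has no VTE, DVT or PE row. There is therefore no stated figure to reproduce, and the inputs below are assumptions.

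Let f be the share of matched warfarin person-time that belongs to patients treated for a current VTE (zero for dabigatran). Let m be their VTE-coded rate relative to the other patients. With a true ratio of 1:

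apparent ratio (dabigatran/warfarin) = 1 / (1 − f + f·m)

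| f | m = 5 | m = 10 |
|---|---|---|
| 1% | 1/1.04 = 0.96 | 1/1.09 = 0.92 |
| 2% | 1/1.08 = 0.93 | 1/1.18 = 0.85 |
| 5% | 1/1.20 = 0.83 | 1/1.45 = 0.69 |

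f must be a share of person-time, not of starters. If 5% of starters contribute half the usual follow-up, then f = 0.025/0.975 = 2.6%. With m = 10 the apparent ratio is 1/(1 + 0.0256 × 9) = 0.81, not 0.69.

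**4. Could it look statistically significant?** The test is first checked against Table 8. For stroke at interim report 1, E0 = 31.59/1,000 × 10,000 = 315.9 events. Solving (RR − 1)·E0 = (1.96 + 0.84)·√(E0(1 + RR)) gives RR = 1.236, against 1.24 stated.

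For VTE at the final report (24,100 person-years per group), let E0 be the expected dabigatran events and Ew = E0(1 − f + f·m). The chance of a falsely significant result in favour of dabigatran is Φ((Ew − E0)/√(Ew + E0) − 1.96), which is 2.5% with no bias.

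Example: an assumed 10 per 1,000 person-years gives E0 = 241. With f = 2% and m = 10, Ew = 284.4, (43.4)/√525.4 = 1.89, and the chance is 47%.

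| Assumed VTE rate per 1,000 PY | f = 2%, m = 5 | f = 2%, m = 10 | f = 5%, m = 10 |
|---|---|---|---|
| 10 | 14% | 47% | 99% |
| 5 | 9% | 27% | 88% |

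**5. Stroke and bleeding.** For these outcomes there is no reason to expect a large m. With m between 0.5 and 2 and f = 5%, the apparent ratio runs from 1/0.975 = 1.03 to 1/1.05 = 0.95.

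**The case against.** The strongest reply is that matching may already deal with this. If recent VTE and joint surgery are in the propensity score, those warfarin starters have low predicted probabilities of dabigatran. Many could then go unmatched under 1:1 matching with a 0.05 caliper, from a pool of about two warfarin starters per dabigatran starter (47,720 against 24,150 in Table 7). Section 1 also lists a high-dimensional propensity score, so an empirical score may be planned in text that is not shown. If recent VTE is tabulated after matching, even 1% against 0% gives a standardized difference of 0.01/√(0.0099/2) = 0.14, above the 0.1 flag. Section 7.9.1 adds that the variables typically imbalanced in Phase 1 were all within HAS-BLED and CHA2DS2-VASc.

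Much of this stands. A reader might infer from 7.3 that the matched comparison is biased, or that the plan omits VTE as a covariate. The documents support neither, because the covariate list and the further analyses are not in the text available. The Phase 1 remark is fair counter-evidence, but it covers only the variables measured, and 7.7 ties the Phase 1 rates to UnitedHealth, which supplies 4,150 of the 24,150 dabigatran starters (17%). A covariate for any history of VTE could also balance in prevalence while mixing old clots on one drug with current clots on the other.

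Three further limits are accepted. A stay that ended before the dispensing is not counted, so a later admission is needed. Table 1 stops at December 2013 while accrual runs to December 2015, so one-sidedness throughout is an expectation. And these patients do have an AF code: what differs is the reason for starting treatment.

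**Conclusion.** The concern holds as a gap in the eligibility rule, with a conditional consequence. Unless the propensity score specifically balances recent VTE and joint surgery, the VTE, DVT and PE results may be biased toward dabigatran.

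The size is unknown. The range of about 0.96 to 0.69 for a true ratio of 1 is an illustration. It rests on an assumed 1% to 5% of matched warfarin person-time, none on dabigatran, and a 5- to 10-fold rate. If the share were equal in both groups, the apparent ratio would return to 1.

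A reader might extend this to the primary outcomes, but the documents do not support that: under the assumptions above, stroke and major bleeding stay within about 0.95 to 1.03. This is a cheap improvement to secondary outcomes, not a flaw in the main comparison.

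**What to change.** For the VTE, DVT and PE analyses, add to 7.3 an exclusion of patients with a Table 2 DVT or PE code, or a hip or knee replacement, in a pre-specified window up to and including the index date. Sixty days is an example; the documents do not supply a window, and the sponsor should justify the choice. Apply the exclusion before matching so that pairs stay intact, and list the joint replacement codes, which the visible code lists do not include.

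Repeat the stroke and major bleeding analyses with the same exclusion as a sensitivity analysis. Alternatively, apply the exclusion to the whole cohort and keep the unrestricted cohort as the sensitivity analysis. Report the number excluded by drug in Figure A1. If few are excluded, or the numbers are similar across drugs, the reader can see that the issue is minor.

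The cost is one criterion built from claims already held, one additional matched analysis, and a loss of initiators that should be small. Some genuine AF patients with a coincident recent VTE will be removed.
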